4.5.2 Dose Modifications

No dose adjustments or changes in intake frequency are allowed for any of the assigned study drugs in the protocol, except for the unique case of treatment-limiting renal toxicity which limits the use of the TDF. In the event of treatment-limiting renal toxicity, dose interval adjustments for TDF are permitted according to the local package insert/label, and only after the completion of the Week 2 Intensive PK optional Visit, if the subject is inclined to participate.

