1.3.2 Secondary Objectives

- To assess the antiviral efficacy of BMS-955176 arms, and TDF-containing regimens (TDF + ATV/r + DTG), by determining the proportion of treatment-experienced subjects with plasma HIV-1 RNA < 40 c/mL at Weeks 48 and 96
- To assess the antiviral efficacy of BMS-955176 arms, and TDF-containing regimens, by determining the proportion of treatment-experienced subjects with plasma HIV-1 RNA < 200 c/mL at Weeks 24, 48, 96

- To assess the emergence of HIV drug resistance in samples selected for drug resistance testing (according to criteria outlined in [Sections 5.4.1.1](#) and [5.4.1.2](#))
- To assess efficacy of BMS-955176 arms, and TDF-containing regimens, by using the mean changes from baseline in \log_{10} HIV-1 RNA, CD4+ T-cell counts, and percentage of CD4+ T-cells
- To assess the safety and tolerability of BMS-955176 in treatment-experienced subjects by measuring frequency of SAEs and AEs leading to discontinuation
- To assess disease progression as measured by the occurrence of new AIDS defining events (CDC Class C events)
- To characterize the pharmacokinetics of BMS-955176 when co-administered with ATV (with or without ritonavir) and DTG in treatment-experienced HIV-1 infected subjects

1.3.3 *Exploratory Objectives*

- To determine the effect of BMS-955176 arms, and TDF-containing regimens, on renal clinical parameters and biomarkers through Weeks 48 and 96
- To determine the effect of BMS-955176 arms, and TDF-containing regimens, on bone biomarkers through Weeks 12 and 24
- To assess the impact of baseline (pre-therapy) Gag polymorphisms on the efficacy of BMS-955176 by determining the proportion of treatment-experienced subjects with plasma HIV-1 RNA < 40 c/mL, HIV-1 RNA < 200 c/mL, and the changes from baseline in \log_{10} HIV-1 RNA at Weeks 24, 48 and 96, by baseline polymorphisms
- To characterize the steady-state plasma PK of DTG when co-administered with BMS-955176 and ATV (with or without RTV) in treatment-experienced subjects. The effect of BMS-955176 on DTG PK in the presence of ATV (without RTV) may be assessed relative to historical data
- To compare steady-state exposures of DTG when co-administered with BMS-955176 and ATV/RTV to DTG when co-administered with TDF and ATV/RTV
- To characterize the PK of ATV when co-administered with DTG and BMS-955176, with or without RTV

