3.1.3 Week 2 Intensive PK Visit

Subjects with anemia, defined as Hemoglobin < 11.0 g/dL, should be excluded from participation in the Week 2 Intensive PK Substudy.

Subjects in all arms will have the opportunity to participate in an elective Intensive PK Substudy visit at Week 2 (window for visit: Day 12-16). Approximately 60 subjects, 12 subjects from each arm, are expected to participate in the substudy; BMS may allow the substudy to over-enroll in an effort to have a sufficient number of complete datasets.

The series of 12 blood draws begins with pre-dose (0-hour) blood samples to be collected approximately 24 hours (20-28 hrs) after the morning doses of study drugs that were taken on the day before. Ten more samplings are drawn through the 12-hr time point, with one final sampling collected at the 24-hr time point, requiring the subject to either remain overnight in the clinic, or to return the next morning; the final 24-hr sample will be collected prior to administration of the morning doses of study drugs (See [Section 5.5.1](#)).

PK Tools/Job Aids will be provided to assist with the proper sequencing of dosing and blood sample collections, as well as the collection of required data.

3.1.4 Visits Week 4 - 96

Subjects are expected to be treated for the duration of 96 weeks. In each Stage, after Day 1 and the optional Intensive PK visit at Week 2, subjects will be required to attend 12 more in-clinic study visits over the 96-week treatment period, as follows:

- Visits are conducted every 4 weeks from Week 4 through Week 16
- Visits are conducted every 8 weeks from Week 24 through Week 48
- Visits are conducted every 12 weeks from Week 60 through Week 96

Visits should be scheduled as an interval from the Day 1/Randomization date, and within a window of 5 days earlier or later.

One of the visits Week 4 - 24 should meet the very specific timing requirements as outlined in [Section 5.5.2](#) for a pre-AM dose blood collection.

Telephonic visits will be conducted with each subject at visit Weeks 20, 28, 36, 44, 54, 66, 78, and 90 to conduct an adherence assessment and to continue retention efforts

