- 4) Failure to have the last on-treatment HIV-1 RNA to < 400 c/mL within Week 24, 48, or 96 week snapshot window
- 5) Failure to achieve $> 1 \log_{10}$ c/mL decrease in HIV-1 RNA by Week 8

In addition to the clinical management outlined in [section 5.4.1.1](#), samples meeting criteria for PDVF will also be sent for resistance and exploratory resistance testing.

5.4.2 *Secondary Efficacy Assessments*

5.4.2.1 *CD4+ and CD8+ T-Cells*

CD4+ and CD8+ T-cells counts and percentages will be assessed using flow cytometry. The schedule of assessments is provided in [Section 5.1](#) (Flow Chart/Time and Events Schedule). Procedures for samples collection and processing are provided in the central clinical laboratory manual.

5.4.2.2 *Drug Resistance Testing*

Plasma samples for viral drug resistance testing will be collected at Screening for all subjects and the HIV-1 drug resistance genotype will be analyzed to rule out resistance to any component of the study regimen or specific resistance mutations as outlined in [Section 3.3.2](#), Exclusionary Criteria. At subsequent visits, samples for emergent drug resistance testing (both genotypic and phenotypic) will be collected and stored to be as outlined in [Section 5.4.1](#).

5.5 *Pharmacokinetic Assessments*

It is extremely important to record the exact dose and time of the dose(s) taken the day prior to the visit/collection, and the exact date and time of the sample collection, even if drawn slightly off-schedule.

5.5.1 *Intensive Pharmacokinetic Assessment*

A subset of subjects (about 12 subjects per treatment group) will participate in an optional Intensive PK assessment at Week 2 (window Day 12-16).

Intensive PK samples collected in this study will provide for the assessment of BMS-955176, ATV, RTV, and DTG to support the secondary and exploratory objectives (to characterize the PK of BMS-955176, DTG, and ATV (with or without RTV) when given in combination, and to compare steady-state exposures of DTG when co-administered with BMS-955176 and ATV/RTV to DTG when co-administered with TDF and ATV/RTV).

Intensive PK sampling begins with a morning pre-dose (0 hour) sampling, ie, prior to the administration of the morning doses of the study drugs on the day of the visit. The sampling should also begin 24 hours (between 20 and 28 hours) after the morning doses of the study drugs that were taken the day prior to the visit.

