The subsequent 11 time points include samplings through Hour 12, with the last sample collected at Hour 24. The subject will either stay overnight or will return to the clinic so that the final sample can be collected at Hour 24.

It is critical to capture the exact date and time of each PK sample collection, even if drawn slightly off-schedule. There is no specified collection window end for which any one time point should be abandoned as the schedule progresses. If a sample collection time point is missed/late and the next collection time point has not yet been reached, collect the missed time point, and record the exact time of that collection, then get back on track for the next time point/on-time collection.

Table 5.5.1-1 lists the sampling schedule to be followed for the assessment of intensive pharmacokinetics. Further details of PK blood collection and sample processing will be provided in the central clinical laboratory manual.

Table 5.5.1-1: AI468048 Intensive Pharmacokinetic Sampling Schedule at Week 2

	Time (Event)	Time (Relative to Dosing) Hour: Min	PK Blood Sample
Study Week 2 (window Day 12-16)	0 (morning pre-dose)	00:00	X
	1 Hr	01:00	X
	2 Hr	02:00	X
	2.5 Hr	02:30	X
	3 Hr	03:00	X
	4 Hr	04:00	X
	4.5 Hr	04:30	X
	5 Hr	05:00	X
	6 Hr	06:00	X
	8 Hr	08:00	X
	12 Hr	12:00	X
	24 hr (morning pre-dose)	24:00	X

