6.3 Laboratory Test Result Abnormalities

The following laboratory test result abnormalities should be captured on the nonserious AE CRF page or SAE Report Form (paper or electronic) as appropriate:

- Any laboratory test result that is clinically significant or meets the definition of an SAE
- Any laboratory test result abnormality that required the subject to have study drug discontinued or interrupted
- Any laboratory test result abnormality that required the subject to receive specific corrective therapy

It is expected that wherever possible, the clinical rather than laboratory term would be used by the reporting investigator (eg, anemia versus low hemoglobin value).

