6.7.1.2 Management of Renal Toxicity

Serum phosphate levels and creatinine clearance (CrCl; CCL: as calculated by the Cockcroft Gault Equation [see [Appendix 4](#)] or eGFR) should be monitored and managed as described in the Viread local package insert/label.²⁸ Dose interval adjustments of TDF (Viread) are permitted, as described in [Section 4.5.2](#).

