9 STUDY MANAGEMENT

9.1 Compliance

9.1.1 *Compliance with the Protocol and Protocol Revisions*

The study shall be conducted as described in this approved protocol. All revisions to the protocol must be discussed with, and be prepared by, BMS. The investigator should not implement any deviation or change to the protocol without prior review and documented approval/favorable opinion from the IRB/IEC of an amendment, except where necessary to eliminate an immediate hazard(s) to study subjects.

If a deviation or change to a protocol is implemented to eliminate an immediate hazard(s) prior to obtaining IRB/IEC approval/favorable opinion, as soon as possible the deviation or change will be submitted to:

- IRB/IEC for review and approval/favorable opinion
- BMS
- Regulatory Authority(ies), if required by local regulations

Documentation of approval signed by the chairperson or designee of the IRB(s)/IEC(s) must be sent to BMS.

If an amendment substantially alters the study design or increases the potential risk to the subject: (1) the consent form must be revised and submitted to the IRB(s)/IEC(s) for review and approval/favorable opinion; (2) the revised form must be used to obtain consent from subjects currently enrolled in the study if they are affected by the amendment; and (3) the new form must be used to obtain consent from new subjects prior to enrollment.

If the revision is done via an administrative letter, investigators must inform their IRB(s)/IEC(s).

9.1.2 *Monitoring*

BMS representatives will review data centrally to identify potential issues to determine a schedule of on-site visits for targeted review of study records.

Representatives of BMS must be allowed to visit all study site locations periodically to assess the data quality and study integrity. On site they will review study records and directly compare them with source documents, discuss the conduct of the study with the investigator, and verify that the facilities remain acceptable. Certain CRF pages and/or electronic files may serve as the source documents:

In addition, the study may be evaluated by BMS internal auditors and government inspectors who must be allowed access to CRFs, source documents, other study files, and study facilities. BMS audit reports will be kept confidential.

The investigator must notify BMS promptly of any inspections scheduled by regulatory authorities, and promptly forward copies of inspection reports to BMS.

9.1.2.1 *Source Documentation*

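### Minor: Section 4.5.2 makes a label-directed TDF interval change for renal toxicity wait for an elective Week 2 PK visit; the condition should be deleted

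*Protocol*

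**What the plan says.** Section 4.5.2 (Dose Modifications) bars every change of dose or frequency, with one exception. If renal toxicity limits the use of TDF, its dosing interval may be changed as the local label directs, "and only after the completion of the Week 2 Intensive PK optional Visit, if the subject is inclined to participate". The sentence is the same in Revised Protocol 02 and in the current Revised Protocol 03.

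Section 6.7.1.2 (Management of Renal Toxicity) makes the label the standard for monitoring and managing renal function. For interval changes it points back: "Dose interval adjustments of TDF (Viread) are permitted, as described in" Section 4.5.2. It therefore carries the same condition.

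Section 3.1.3 describes the Week 2 visit as elective, with a Day 12-16 window and about 12 participants per arm. Section 5.5.1 ends the profile with a 24-hour sample: "The subject will either stay overnight or will return to the clinic so that the final sample can be collected at Hour 24". It names what is measured: "Intensive PK samples collected in this study will provide for the assessment of BMS-955176, ATV, RTV, and DTG". Tenofovir is not on that list.

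**The concern.** A subject on TDF who develops treatment-limiting renal toxicity before the Week 2 visit, and who has joined the substudy, may not have the interval changed until the PK profile is complete. That puts completion of an elective research procedure ahead of a safety step for which the protocol otherwise defers to the label. It also sits badly with the statement in Section 2.3 that subjects' safety prevails over the interests of science.

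At stake is the handling of a few subjects over roughly the first two weeks of dosing. No statistical quantity in the trial depends on it.

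**Working it through.** The plan gives no figure here to reproduce. The check is a reading of the text plus some day counting.

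**Does the PK purpose need the condition?** The listed analytes are BMS-955176, ATV, RTV and DTG (Section 5.5.1). A changed TDF interval therefore alters no measured TDF profile. What it could disturb is one exploratory objective in Section 1.3.3: "To compare steady-state exposures of DTG when co-administered with BMS-955176 and ATV/RTV to DTG when co-administered with TDF and ATV/RTV". There TDF helps to define the reference condition, so a subject on an altered schedule would make that reference group less uniform. Leaving that subject out of the comparison restores uniformity without delaying care.

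**How long can the wait be?**
- Last day of the visit window: Day 16 (Section 3.1.3).
- Final sample 24 hours later: Day 16 + 1 = Day 17.
- Dosing starts on Day 1 (Section 3.1.2.1), so the upper bound is 17 − 1 = 16 days. A real wait would be shorter, because it runs from the onset of toxicity.

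**How many subjects can it reach?**
- Stage 1: about 12 of about 40 TDF subjects (Arm 2).
- If Stage 2 opens: 12 + 12 = 24 of 40 + 40 = 80 (Arms 2 and 5).
- These are substudy participants on TDF, not expected cases.

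**Would the toxicity be seen in that time?**
- Chemistry, including creatinine and phosphorus, is scheduled on Day 1 and next at Week 4 (Appendix 5). None is scheduled at Week 2.
- With the 5-day visit window, the earliest Week 4 draw is Day 28 − 5 = Day 23, or Day 29 − 5 = Day 24 if Week 4 is counted as 28 days after Day 1.
- That is 23 − 17 = 6 or 24 − 17 = 7 days after the latest PK sample.
- No scheduled post-dose chemistry falls before Day 17, so the clause can act only on an unscheduled finding.
- Section 3.3.2 excludes an eGFR below 60 mL/min at entry, which lowers the chance further. The protocol gives no rate for early renal events.

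**What would removing the condition cost the PK analysis?** Losing one profile of 12 is 1/12 = 8.3%; losing two is 2/12 = 16.7%.

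**The case against.** The strongest reply is that the clause releases itself. The visit is elective and the condition applies only to a subject inclined to take part, so someone with renal toxicity can skip the visit and have the interval changed at once. That reading is plausible, and it is the main reason the practical harm is small. The text does not state it, though, and no instruction tells a site that a subject who needs the change should forgo the visit.

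Other routes are also open. Section 3.5 requires discontinuation when the investigator judges that continuing is not in the subject's interest. Section 9.1.1 permits an unapproved deviation "except where necessary to eliminate an immediate hazard(s) to study subjects". Section 6.3 contemplates interruption, since it lists for recording "Any laboratory test result abnormality that required the subject to have study drug discontinued or interrupted", but it is a recording rule and authorises nothing by itself. Stopping the drug, or invoking a hazard exception, is a heavier step than the interval change being held back.

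It can also be said that TDF defines the reference regimen for the dolutegravir comparison, so its schedule matters even though it is not assayed. That is correct, and it is why the remedy includes an exclusion rule. It does not justify holding the adjustment.

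Finally, the label is not among the documents, so one cannot confirm that it would call for an interval change, rather than stopping, so early in treatment. That stands as a limit on how often the clause could matter. It does not rescue the wording, because the protocol itself makes the label the standard and then delays its use.

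**Conclusion.** The concern holds, as a minor one. Section 4.5.2 makes the only permitted dose modification wait, for substudy participants on TDF, until an elective PK visit is finished, and the PK objective does not require that.

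The reach is at most about 12 of 40 TDF subjects in Stage 1, or 24 of 80 over both stages, with a wait of up to about 16 days. The number actually affected may well be zero, since it takes an unscheduled renal finding before Day 17 in subjects who entered with an eGFR of at least 60 mL/min. These figures assume the planned 12 participants per arm and the stated visit windows. No efficacy estimate, confidence interval or futility comparison is touched.

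**What to change.** At the next amendment, delete the condition quoted above from Section 4.5.2. Section 6.7.1.2 then needs no edit, because it only refers back.

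Add one sentence to Section 5.5.1, for example: *A subject whose TDF interval is changed before completion of the Week 2 profile is excluded from the intensive-PK DTG comparison, and the number excluded is reported.* A lighter alternative is to keep the sentence in Section 4.5.2 and state that a subject who needs the change receives it at once and skips the intensive-PK visit.

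The cost is one clause removed, one sentence added, and possibly one or two of about 12 profiles in an arm (8% or 17%). Replacement is possible but not assured, since Section 3.1.3 says only that "BMS may allow the substudy to over-enroll in an effort to have a sufficient number of complete datasets".

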4.6 Blinding/Unblinding

Not applicable.

4.7 Treatment Compliance

Treatment Adherence to the treatment regimen will be critical to the conduct of this study. Adherence will be evaluated by the investigative staff at every treatment visit (including telephone contact visits) through interviews with the subjects and through examination of returned medication. It is expected that site staff attempt to have subjects maintain 90% treatment compliance or greater. Subjects should be instructed to bring all unused study medication back in the original container to each visit. Site staff are required to review Dosing Diaries completed by the subject, and to reinforce their use.

4.8 Destruction of Study Drug

For this study, study drugs (those supplied by BMS or sourced by the investigator) such as partially used study drug containers, vials and syringes may be destroyed on site.

Any unused study drugs can only be destroyed after being inspected and reconciled by the responsible Study Monitor unless study drug containers must be immediately destroyed as required for safety, or to meet local regulations (eg, cytotoxics or biologics).

On-site destruction is allowed provided the following minimal standards are met:

- On-site disposal practices must not expose humans to risks from the drug
- On-site disposal practices and procedures are in agreement with applicable laws and regulations, including any special requirements for controlled or hazardous substances
- Written procedures for on-site disposal are available and followed. The procedures must be filed with the site's SOPs and a copy provided to BMS upon request

- Records are maintained that allow for traceability of each container, including the date disposed of, quantity disposed, and identification of the person disposing the containers. The method of disposal, ie, incinerator, licensed sanitary landfill, or licensed waste disposal vendor must be documented
- Accountability and disposal records are complete, up-to-date, and available for the Monitor to review throughout the clinical trial period

If conditions for destruction cannot be met the responsible Study Monitor will make arrangements for return of study drug.

It is the investigator's responsibility to arrange for disposal of all empty containers, provided that procedures for proper disposal have been established according to applicable federal, state, local, and institutional guidelines and procedures, and provided that appropriate records of disposal are kept.

4.9 Return of Study Drug

If study drug will not be destroyed upon completion or termination of the study, all unused and/or partially used study drug that was supplied by BMS must be returned to BMS. The return of study drug will be arranged by the responsible Study Monitor.

It is the investigator's responsibility to arrange for disposal of all empty containers, provided that procedures for proper disposal have been established according to applicable federal, state, local, and institutional guidelines and procedures, and provided that appropriate records of disposal are kept.

5 STUDY ASSESSMENTS AND PROCEDURES

5.1 Flow Chart/Time and Events Schedule

Table 5.1-1: Screening Procedural Outline (AI468048)

Procedure	Screening Visit (42-day screening period) ^a	Notes
Eligibility Assessments		
Informed Consent	X	
Call IVRS to Enroll the subject; PID assigned	X	
Inclusion/Exclusion Criteria	X	
Medical History	X	
AIDS History	X	
Non-Laboratory Safety Assessments		
Full Physical Examination	X	See Section 5.3.1 for requirements
Vital Signs & Physical Measurements	X	See Section 5.3.1 for requirements
Pre-treatment events	X	Only CDC Class C events with onset during the Screening period
Serious Adverse Events Assessment	X	All SAEs that occur after the ICF has been signed should be reported
ECG	X	See Section 5.3.4 for requirements
Pregnancy Test	X	
WOCBP
 
For females under age 55, an FSH level must be on record to confirm she is not a WOCBP if pregnancy testing is not being performed.
 
If positive urine, request serum hCG quant. on lab requisition.

Laboratory Assessments (See Appendix 5 for full details)		
Fasting Chemistry and Lipid Panel	X	Fasting overnight
Hematology	X	
Urinalysis	X	

Table 5.1-1: Screening Procedural Outline (AI468048)

Procedure	Screening Visit (42-day screening period) ^a	Notes
Plasma HIV-1 RNA	X	This is the confirmatory HIV-1 RNA (The first value is provided by the PI)
CD4+ and CD8+ T-cell count	X	
HBV Surface Antigen	X	
HCV Serology	X	
Urine toxicology (drugs of abuse)	X	Could aid in the selection of appropriate study candidates.
Pharmacodiagnostic (PDx) sample ^b	X	Plasma collection to be banked for potential future use in development of novel predictive assay(s)
Resistance Testing (HIV-1 Drug Resistance)		
PhenoSense GT Plus Integrase	X	Proper collection of the full volume of plasma outlined in the lab manual will allow for repeat testing of the sample if assay steps fail during testing. ^a
PhenoSense Gag	X	
Next Generation Seq. - Qs Gag	X	
Exploratory Resistance (HIV-1 Drug Resistance)	X	Molecular analysis at BMS WFD Discovery of baseline resistant samples and baseline sensitive controls in cases of subsequent on-treatment virologic failure

^a If the PSGT + Integrase resistance assay cannot be resulted within 42 days, the Screening window can be extended up to 60 days, and solely for this procedure to allow time for Monogram to complete the testing.

^b By definition, a pharmacodiagnostic sample (PDx) is a pre-treatment test to determine whether or not a patient is likely to respond to a drug (ie, a predictive test). Based on the results of clinical studies with BMS-955176, BMS may have to develop a PDx assay. Thus, PDx samples obtained at Screening in this study would be used for that sole purpose.

Table 5.1-2: Short-term Procedural Outline (AI468048)

Procedure	In-clinic Visit Day 1	In-Clinic Visit Optional Week 2 for Intensive PK (Day 12-16)	In-Clinic Visits Weeks 4, 8, 12, 16, 24, 32, 40, 48, 60, 72, 84, 96, and/or Early Termination (ET) (± 5 days)	Phone Visits Weeks 20, 28, 36, 44, 54, 66, 78, 90 (± 5 days)	Notes
Eligibility Assessments					
Inclusion/Exclusion Criteria	X				
Non-Laboratory Safety Assessments					
Full Physical Examination			WK 12, 24, 48, 96/ET		See Section 5.3.1 for requirements
Targeted Physical Examination	X		WK 4, 8, 16, 32, 40, 60, 72, 84		See Section 5.3.1 for requirements
Vital Signs & Physical Measurements	X		X		See Section 5.3.1 for requirements
Adherence Assessments			X	X	Including review of Dosing Diaries
Pre-treatment Events	X				See Table 5.1-1
Adverse Events Assessments	X	X	X		Serious and Non-serious AEs
Concomitant Medications	X	X	X		See Section 5.3.3
ECG	X		WK 4, 12, 24, 48, 96/ET		See Section 5.3.4 for requirements
Pregnancy Test	X	X	X		For females under age 55, an FSH level must be on record to confirm she is not a WOCBP if pregnancy testing is not being performed. If positive urine, request serum hCG quant. on lab requisition.

Table 5.1-2: Short-term Procedural Outline (AI468048)

Procedure	In-clinic Visit Day 1	In-Clinic Visit Optional Week 2 for Intensive PK (Day 12-16)	In-Clinic Visits Weeks 4, 8, 12, 16, 24, 32, 40, 48, 60, 72, 84, 96, and/or Early Termination (ET) (± 5 days)	Phone Visits Weeks 20, 28, 36, 44, 54, 66, 78, 90 (± 5 days)	Notes
Provide WOCBP with Home Pregnancy test kit(s) to be used during the in-clinic visit interval			WK 16, 24, 32, 40, 48, 60, 72, 84		Provide One Kit at Weeks 16 - 40 Provide Two Kits at Weeks 48 - 84 WOCBP subjects perform test Q4 weeks at home and report results to site.
Laboratory Assessments for Safety and Efficacy and Other Endpoints (See Appendix 5 for full details)					
Fasting Chemistry	X		X		Fasting overnight
Fasting Lipid Panel	X		WK 4, 12, 24, 48, 96/ET		Fasting overnight
Hematology	X		X		
Urinalysis	X		X		
Fractional Excretion of Phosphorous (FePO4) (Urine creatinine and phosphorus, Serum creatinine and phosphorus)	X		WK 48 and 96/ET		
Plasma HIV-1 RNA	X	X	X		If collecting an HIV-1 RNA at an UNSCHEDULED visit, also collect samples for Resistance and Exploratory Resistance Testing
CD4 and CD8 T-cell counts	X		X		
HBV Surface Antigen			WK 48 and 96/ET		
HCV Serology			WK 48 and 96/ET		Positive HCV Ab will reflex to HCV RNA

Table 5.1-2: Short-term Procedural Outline (AI468048)

Procedure	In-clinic Visit Day 1	In-Clinic Visit Optional Week 2 for Intensive PK (Day 12-16)	In-Clinic Visits Weeks 4, 8, 12, 16, 24, 32, 40, 48, 60, 72, 84, 96, and/or Early Termination (ET) (± 5 days)	Phone Visits Weeks 20, 28, 36, 44, 54, 66, 78, 90 (± 5 days)	Notes
Resistance Testing (HIV-1 Drug Resistance)					
PhenoSense GT Plus Integrase	X		X		Samples stored and tested if needed (ie, analyses of subjects if deemed clinically relevant) See Section 5.4.2.2
PhenoSense Gag	X		X		
Next Generation Seq. - Qs Gag	X		X		
Exploratory Resistance (HIV-1 Drug Resistance)	X		X		Samples stored and tested retrospectively if needed (ie, exploratory analyses for subjects if deemed clinically relevant)
Intensive PK sample collection		X			Use of PK Tools for data collection recommended. See Section 5.5.1 for requirements
Sparse PK sample collection			WK 4, 8, 12, 16, 24		See Section 5.5.2 for requirements
Bone Biomarkers (PINP and CTX)	X		WK 12 and 24/ET		Serum collection
Renal Biomarkers (β2-microglobulin and creatinine)	X		WK 48 and 96/ET		Urine collection
Backup Serum and Plasma Sample	X		X		Samples stored and tested if needed
Outcomes Measures					
EQ-5D-3L Form	X		WK 12, 24, 32, 40, 48, 60, 72, 84, 96		Health Outcomes Questionnaire

Table 5.1-2: Short-term Procedural Outline (AI468048)

Procedure	In-clinic Visit Day 1	In-Clinic Visit Optional Week 2 for Intensive PK (Day 12-16)	In-Clinic Visits Weeks 4, 8, 12, 16, 24, 32, 40, 48, 60, 72, 84, 96, and/or Early Termination (ET) (± 5 days)	Phone Visits Weeks 20, 28, 36, 44, 54, 66, 78, 90 (± 5 days)	Notes
FAHI Form	X		WK 12, 24, 32, 40, 48, 60, 72, 84, 96		Functional Assessment of HIV Infection
Clinical Drug Supply					
Call IVRS to Randomize	X				
Dispense Study Drug	X		X		There is no dispensation at Week 96 or ET.

5.1.1 *Retesting During Screening or Lead-in Period*

Retesting of laboratory parameters and/or other assessments within any single Screening or Lead-in period will be permitted (in addition to any parameters that require a confirmatory value). The Screening Period for this study is 42 days (see [Table 5.1-1](#), Table Note a, for the single parameter for which the screening period may be extended).

Any new result will override the previous result (ie, the most current result prior to Randomization) and is the value by which study inclusion will be assessed, as it represents the subject's most current, clinical state.

Laboratory parameters and/or assessments that are included in Table 5.1-1, Screening Procedural Outline may be repeated in an effort to find all possible well-qualified subjects. Consultations with the Medical Monitor may be needed to identify whether repeat testing of any particular parameter is clinically relevant (eg, a previously failed inclusion criterion).

Rescreening is different than Retesting. Rescreening is the process of Re-enrollment and requires that all procedures be repeated in an entirely new screening period. A one-time Rescreening is permitted, if further rescreening is considered for reassessment of enrollment eligibility this should be discussed with the Medical Monitor.

The assigned patient identifier (PID) for the subject must be Screen Failed in the IVRS. A new call must be made to the IVRS for the assignment of a new PID for the subject, and all Screening parameters must be done again in reference to the new PID (See [Section 3.3.1](#), Inclusion Criteria 2f). Subject must also be re-consented with the new PID.

5.2 *Study Materials*

The sponsor will provide each investigative site with the following:

- BMS-955176 Investigator Brochure (IB) and any relevant safety addenda or updates
- Protocol and any Amendments to the Protocol
- Instructions for completing electronic Case Report Forms (eCRFs)
- Laboratory Manual from the central laboratory
- ECG Machines and manual
- IVRS Worksheets to complete when calling the IVRS center to enroll, randomize, and discontinue subjects
- Patient-reported Outcomes Questionnaires: EQ-5D-3L Health Outcome Questionnaire, FAHI (Functional Assessment of HIV Infection)
- PK Tools/Job Aids that may be used for detailed instruction about the PK visits, and as a comprehensive source for documents of date/times of dosing and blood sampling
- Dosing Diaries
 - Completion by subjects is required
 - Should include daily dose of study medications administered by subject, modified or missed

- Site staff should review the diaries with the subject at each visit, and, in combination with detailed questioning, should be able to provide comprehensive information in the case report form, noting discrepancies in the subject's file. Dosing Diaries should be maintained in the subject's study file.

